## 4. ENROLLMENT & RANDOMIZATION

Participants with fibromyalgia will be enrolled in outpatient physical therapy clinics: half of the clinics will be randomized to TENS+PT and the other half will be randomized to PT only. At each site, individualized PT treatment specified by the physical therapist alone or with TENS will be applied during each visit. Participants in the TENS+PT intervention clinics will receive TENS units and electrodes at baseline to be applied to the cervical and lumbar regions. They will take the units home and bring the units back to their PT clinic visits with instructions for use at home while active and during their exercises. The physical therapist at each clinic will complete routine documentation of treatment that will include the patient-specific functional scale (PSFS) at the intake visit and approximately monthly intervals.

This will be a cluster randomized pragmatic trial. A stratified randomization procedure by healthcare system and size of clinic will be used to randomize clinics to either TENS+PT or PT alone. Half of the clinics will be randomized to TENS+PT and the other half of the clinics will be randomized to PT only.

We hypothesize that using TENS in a PT setting is feasible and that FM patients using TENS in addition to their PT will have reduced movement-evoked pain and other symptoms and are more likely to reach their therapeutic goals and reduced medication use compared to those patients in the PT alone group.

## 5. TABULATIONS

All study participants who provide informed consent will be accounted for in this study. The number of randomized participants with baseline data and their study disposition will be reported overall, and by treatment group. A CONSORT diagram summarizing the final status of all study participants will be provided. The proportion of randomized study participants completing each visit will be summarized as in Table 5.1 below.

**Table 5.1: Completeness of Study Data by Visit**

Visit	TENS+PT (N = XX)	PT Only (N = XX)
BL (Day 1)	XX (XX%)	XX (XX%)
V01 (Day 30 ± 5)	XX (XX%)	XX (XX%)
V02 (Day 60 -5/+10) Primary Endpoint	XX (XX%)	XX (XX%)
V03 (Day 65 ± 5)	NA	XX (XX%)
V04 (Day 90 ± 5)	XX (XX%)	XX (XX%)
V05 (Day 180 ± 5)	XX (XX%)	XX (XX%)

Additional summary reports will describe:

- Number of study participants eligible, consented, and completed their day 1 home activities by site
- Reasons for exclusion
- Completeness of study visits, case report forms
- Protocol deviations
- Study Treatment (TENS) Suspensions
- Early Study Terminations
- Reportable Events
- Study Treatment Compliance
- Baseline participant data will also be summarized by treatment group (PT+TENS and PT only) with respect to important demographic characteristics. Distribution of numeric and categorical variables will be tabulated by treatment group and overall. Numeric variables will be summarized by the mean, standard deviation, minimum, and maximum. Categorical variables will be tabulated by frequency count and percentages. Variables that will be summarized include:
- Demographic Characteristics:
  - Age
  - Gender
  - Race
  - Ethnicity
  - FM Duration (Years)

- FM Characteristics
  - FM disease activity (FIQR)
  - Opioid use at baseline
  - Use of FM Medications

## 6. ANALYSIS POPULATIONS

### 6.1. Primary and Secondary Effectiveness Analyses (6 Month Treatment Period)

#### 6.1.1. Intent-to-Treat (ITT) Population

For the primary outcome as well as all secondary outcomes during the 6 months follow-up period, all analyses will be performed consistent with the intention-to-treat (ITT) principle – per the recent JAMA Guide to Statistics and Medicine (Detry, 2014). With treatment randomization having occurred at the practice site level, the act of signing the consent automatically assigns a participant to the treatment arm the practice site was randomized to. However, it is possible that after signing consent that an enrolled participant will not show up at the PT clinic at day 1 or will not complete the home activities at day 1 where baseline measurements are obtained.

Therefore, such a patient will be a “no-show” for the rest of the study duration. Thus, we will employ a modified ITT definition (mITT), such that the mITT population will include all participants assigned to a study arm that have completed baseline (day 1) home activities. All participants will be analyzed as-randomized, which means they will be analyzed based on the treatment to which they were randomized (whether the clinic is randomized to PT only or PT+ TENS), whether or not they remained compliant with respect to using their randomized TENS group assignment.

#### 6.1.2. Per Protocol (PP) Population

To assess the sensitivity of key results and to obtain knowledge regarding the potential effects when the protocol was strictly adhered to, we will also replicate all key primary, secondary, and additional secondary effectiveness objectives using a per-protocol population. The per-protocol population includes the subset of all mITT participants who satisfy the following:

- Completed more than one PT appointment.
- And in addition, for those in the TENS group
  - Used TENS on at least 8 days within the first 30 days following day 1 homework assignment, and with an average of at least 30 minutes per day for the 30-day period (i.e. have accumulated a minimum of 15 hours of TENS use;  $0.5 \text{ hr} \times 30 = 15 \text{ hours} = 900 \text{ minutes}$ ),

AND

- Used TENS on at least 8 days during the subsequent 30 days (days 31–60), with an average of at least 30 minutes per day for the 30-day period (i.e. have accumulated a minimum of 15 hours of TENS use during days 31 to 60).

The above conditions for those in the TENS group to meet protocol assure continuous adherence of TENS use over the 60-day period.

Those in the TENS group who did not meet the definition of per protocol, 1) met criteria only for the first 30 days but not the second 30 days, or 2) provided TENS usage information but did not meet criteria for usage in both time periods, and 3) did not have any TENS usage information beyond the first day will be included in a dose response analysis of TENS.

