4.4 Participant Withdrawal Criteria

Participants may be withdrawn from the trial for any number of reasons, including participant request or adverse events. If the patient does not complete their baseline assessment prior to their 3rd PT visit, they will be withdrawn from the study. If a participant wants to stop TENS use, they will be encouraged to remain in the study off study intervention and to complete the patient-reported outcomes assessments at the scheduled intervals. Study staff team members will contact the participant to determine the reason for withdrawal and complete the treatment termination CRF. There is no plan to replace participants who stop treatment. Ongoing contact including study newsletters will be used to minimize loss to follow-up and missing data.

Providing TENS units to those participants randomized to no TENS following the day 60 primary endpoint is an additional strategy to minimize missing data and loss to follow-up.

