5.4 Prohibited Concomitant Interventions

5.4.1 Prohibited Interventions

Participants enrolled in a clinic randomized to no TENS will be asked to not use TENS therapy during the first 60 days of study participation. After the 60-day collection of the primary endpoint, participants in no TENS clinics will be given TENS units with instructions on how to use the device.

Participants will not be required to change any of their prescribed medications during the study and no specific medications will be prohibited.

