6 CLINICAL EVALUATIONS/STUDY PROCEDURES

6.1 Schedule of Activities

Evaluation	First and Second PT Intake Visit*	Research Homework before PT Visit 3 (Day 1 ¹)	Treatment Visits	30 +/- 5 days Home ¹	60 - 5/+10 days Home ¹	65 - 5/+15 days Home (No TENS Group Only) ⁴	90 +/- 5 days Home ¹	180 +/- 5 days Home ¹
Eligibility Screen- REDCap™	X							
PSFS		X		X	X		X	X
Informed Consent/ eConsent Review	X*							
Resting NRS pain/fatigue ²		X		X	X	X	X	X
Sit and Stand Test with NRS pain and fatigue pre-treatment ³		X		X	X	X	X	X
TENS applied (or not) x 30 minutes		X	X	X	X	X	X ³	X ³
Demographics		X						
2016 FM Criteria		X						
FIQR		X		X	X		X	X
MAF		X			X			X
BPI		X		X	X		X	X
PROMIS-Physical Function		X		X	X		X	X
PROMIS-Sleep		X		X	X		X	X
PCS		X		X	X		X	X
PHQ-8		X		X	X		X	X
GAD-7		X		X	X		X	X
RAPA		X			X			X
PGIC				X	X		X	X
TAPS1		X			X			X

Concomitant Medications		X						X
Sit and Stand Test with NRS pain and fatigue post TENS or no TENS treatment after 30 min of answering questionnaires		X		X	X	X	X ³	X ³
Adverse Events				X	X		X	X
Barriers to TENS								X

* *Informational activities (e.g., video explaining study, description of TENS) will be delivered at home between PT visits. Consent will be obtained electronically before or as the initial activity of the second PT visit. After the second PT visit, participants will complete Research Homework. Day 1 is designated as the day the baseline study data is collected at home. Baseline data collection should be completed within 10 days of the second PT visit.*

¹*Assessment completed on computer or tablet, phone, or paper at home. If the participant does not have access to a computer, the data will be collected over the phone by the study team and directly entered into the database, or on paper/mailed or Faxed.*

²*Resting NSR pain/fatigue and Sit and Stand Test completed pre and post TENS treatment.*

³*All participants apply TENS*

⁴*Day 65 visit is only performed by the No Tens group*

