6.2.1 First and Second PT Intake Visit

First Visit

- PT identifies possible participant
- Complete eligibility screen on REDCap™, if interested
- If eligible, PT instructs participant to complete electronic consent before PT Clinic Visit 2.
- Provide study information, refer to study website and provide contact for study team.
- When consent is complete REDCap™ sends email to PT and study team.

Second Visit

- PT verifies eConsent completion by email or REDCap™. If consent is not complete, participant may decline or may complete eConsent in clinic before study procedures begin.
- PT provides instructions on:
 - Logging into REDCap™ and accessing forms
 - The importance of the Sit and Stand test and Research Homework
 - TENS use (if applicable)
- Complete PT treatment with physical therapist.
- PT provides TENS units, electrodes, and written brochures to TENS group.
- PT logs TENS unit serial numbers.
- Redcap link emailed to participant to complete Research Homework before PT Clinic Visit 3.

6.2.2 Day 1 Research Homework Before PT Visit 3

- Log into REDCap™ (if participant does not have access to the internet, data collection may be completed on paper and mailed or faxed to study team, or completed by phone with a study team member)
- Pre-treatment resting NRS for pain and fatigue
- Pre-treatment Sit and Stand Test with NRS for pain and fatigue.
- TENS applied (or not) for at least 30 min while completing the assessments below on tablet (no TENS participants go directly to completing the assessments)
- Complete the following assessments on REDCap™:
 - Demographics
 - 2016 FM Criteria
 - PSFS
 - FIQR
 - MAF

- BPI
- PROMIS-Physical function
- PROMIS-Sleep + Sleep duration
- PCS
- PHQ-8
- GAD-7
- RAPA
- TAPS1
- Medications
- Post-treatment resting NRS for pain and fatigue
- Post-treatment Sit and Stand Test with NRS for pain and fatigue
- REDCap™ sends email to PT and study team when Research Homework is complete

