## 1. STUDY DESIGN

### 1.1 Design

This study is a cluster-randomized pragmatic trial conducted where the initial proposed sample size was 600 across 24 physical therapy clinics. The original sample size was reduced from 600 based on a planned interim sample size recalculation following enrollment of the first ~200 participants and based on the planned interim assessment of intra-class correlation coefficient (ICC). A stratified randomization of practice sites will be employed based on healthcare system and size of the practice site (clinics) so that half of the clinics will provide transcutaneous electrical nerve stimulation (TENS) in addition to physical therapy (PT) (TENS+PT) for each enrolled participant and the other half of the clinics will provide standard of care routine individualized PT treatment (PT only). To avoid potential exposure to TENS in the clinics randomized to PT only, the clinics will be specifically instructed not to prescribe TENS to their fibromyalgia (FM) patients. Likewise, study participants in the PT only site that may be exposed to TENS through other means (relatives, friends) will also be instructed not to use TENS to prevent cross-ins. Furthermore, participants randomized to the PT only group will receive TENS unit after the primary outcome data is collected at day 60 which may also prevent cross-ins and provide equipoise. Primary analyses will be based on modified intention-to-treat which includes all participants with baseline (day 1) pre-TENS home activities.

Participants will be followed for 180 days with data collection from home at 1, 30, 60, 90, and 180 days following enrollment. Participants in the PT only group will also complete a brief assessment at day 65. The primary outcome variable will be assessed at day 60, which would be approximately at the completion of prescribed PT. Data collected at PT visits will include the types of treatments (CPT codes) and, at the clinic's usual intervals, visit type (in-person vs telemedicine), and the Patient-Specific Functional Scale (PSFS). All patient reported measures will be obtained at home via computer, tablet, or phone.

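### The per-protocol set has no TENS-use condition for PT-only participants, and its one shared criterion removes nobody if PT visits 1 and 2 count

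*SAP*

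**What the plan says.** SAP 6.1.2 defines the PP set as a subset of the mITT set and plans to repeat the key primary and secondary analyses in it, to learn what the effect is when the protocol is followed closely.

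- **Both arms:** "Completed more than one PT appointment". No start or end is given, and the SAP does not say whether the two visits before baseline count.
- **TENS arm only:** at least 8 days of use and at least 15 hours in total, in the first 30 days and again in days 31 to 60.
- **PT-only arm:** no further condition.

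Entry to mITT is set in SAP 6.1.1: "the mITT population will include all participants assigned to a study arm that have completed baseline (day 1) home activities". Protocol 6.1 places that homework after two PT visits: "After the second PT visit, participants will complete Research Homework". Protocol 6.2.1 lists, for the second visit, "Complete PT treatment with physical therapist". Protocol 4.4 adds: "If the patient does not complete their baseline assessment prior to their 3rd PT visit, they will be withdrawn from the study".

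The PT-only arm has one rule of its own. Protocol 5.4.1: "Participants enrolled in a clinic randomized to no TENS will be asked to not use TENS therapy during the first 60 days". SAP 1.1 repeats it for outside exposure: "participants in the PT only site that may be exposed to TENS through other means (relatives, friends) will also be instructed not to use TENS".

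**The concern.** A per-protocol analysis should apply each arm's own requirements to that arm. Here the TENS arm is held to dated usage minimums, while a control participant who broke the only rule specific to the control arm is kept. Section 3 of the protocol foresees such use, so the case is not hypothetical in principle, although no rate is given.

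The shared PT criterion may also do no work. Two programmers following SAP 6.1.2 could build different PP sets, depending on whether they count the intake visits.

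At stake is the meaning of a sensitivity analysis that the SAP applies to all key objectives. Settling the definition before database lock keeps it from being chosen after results are seen.

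**Working it through.** **The plan's own figure.** The usage minimum is 0.5 h × 30 days = 15 h = 900 minutes per 30-day block, as SAP 6.1.2 states. This is the only arithmetic in the rule and it is correct.

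**Step 1: does the shared criterion remove anyone?** The sequence is visit 1 (intake), visit 2 (includes PT treatment), Day 1 homework, mITT entry, PP. More than one appointment means at least 2. The visits still needed after Day 1 depend on the reading:

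| Visits counted | Already attended at mITT entry | Still needed |
|---|---|---|
| Visits 1 and 2 both count | 2 | 2 − 2 = 0 |
| Count from visit 2 | 1 | 2 − 1 = 1 |
| Count only after Day 1 | 0 | 2 − 0 = 2 |

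Under the first reading, everyone who followed the protocol sequence meets the criterion on entering mITT. The documents give no distribution of visits, so the number removed under the other two readings cannot be computed.

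**Step 2: can control TENS use be identified from planned data?**
- Section 3 of the protocol plans a question about TENS use to every participant at study completion. No recall period is stated. At Day 180 it follows about 120 days of supplied TENS (Protocol 5.1).
- CPT codes show what the clinic delivered, not private use.
- The Day 30 and Day 60 form (Protocol 7.1) asks about problems with TENS, not use.
- Device data (Protocol 5.5) come from study units, which controls do not have before Day 60.

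The information is therefore partial, with the completion question as the main source.

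**Step 3: effect of keeping control users.** Let c be the share of controls who used TENS and e its effectiveness in them relative to the TENS arm, with e no greater than 1. The documents give neither, so both are assumed. Taking the design difference of 1.0 point, the contrast is 1.0 × (1 − c × e).

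| c | Contrast, e = 1 | Shrinkage | Contrast, e = 0.5 | Shrinkage |
|---|---|---|---|---|
| 5% | 0.95 | 0.05 | 0.975 | 0.025 |
| 10% | 0.90 | 0.10 | 0.95 | 0.05 |
| 20% | 0.80 | 0.20 | 0.90 | 0.10 |

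**Step 4: effect of removing them.** Removing users selects after assignment. If the tendency to use TENS correlates r with the outcome (assumed normal, SD 2.0 from the sample-size section), the mean of the remaining controls shifts by |r| × 2.0 × φ(z)/(1 − c). Here z is the upper-c normal quantile and φ(z)/(1 − c) is 0.109, 0.195 and 0.350 for the three values of c.

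| c | r = 0.1 | r = 0.2 | r = 0.3 |
|---|---|---|---|
| 5% | 0.02 | 0.04 | 0.07 |
| 10% | 0.04 | 0.08 | 0.12 |
| 20% | 0.07 | 0.14 | 0.21 |

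For example, c = 20% and r = 0.3 gives 0.3 × 2.0 × 0.350 = 0.21. The sign of r is unknown, so the direction of the shift is too.

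**The case against.** The strongest objection is that excluding control users is not clearly better than keeping them. Steps 3 and 4 give effects of similar size. With half-effective TENS and r = 0.2, the selection shift (0.04, 0.08, 0.14) exceeds the shrinkage (0.025, 0.05, 0.10) in every row. This stands. It is why the result should be shown both with and without the condition.

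A reader might infer that control TENS use must pull the PP contrast toward zero. The documents do not support that. Users select themselves and may differ in outcome, so the net direction is unknown. Full effectiveness is also an upper bound: the TENS-arm Day 60 rating follows 30 minutes of TENS, and a control assessed without a session would not ordinarily gain that effect from past use.

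A reader might also infer that qualifying visits could routinely fall after Day 60. The wording allows it, but Protocol 5.1 expects about 6 weeks of PT, so the case is remote.

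Two further points have some force. Exposure is limited by the exclusion for TENS use in the previous 30 days, by the instructions to clinics and participants, and by supplying units only after Day 60. Excluding a control for any use is also stricter than the TENS arm's 8-day, 15-hour minimum. However, the control rule in the protocol is no use at all, so any reported use is its direct counterpart.

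Section 3 of the protocol says the sample is believed large enough to absorb cross-in exposure. That bears on the main comparison and does not define the PP set.

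**Conclusion.** Both gaps stand. Followed exactly, SAP 6.1.2 keeps PT-only participants who breached their one arm-specific rule. Its only shared criterion removes nobody if visits 1 and 2 count, which the SAP leaves open. That conclusion assumes the protocol's visit sequence was followed.

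The numerical effect cannot be computed. At assumed control use of 5% to 20%, retention could shrink a 1.0-point contrast by at most 0.05 to 0.20. Removal could shift it by 0.02 to 0.21 either way for assumed correlations of 0.1 to 0.3. These figures illustrate scale and do not show which version is nearer the truth.

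Nothing here touches the primary analysis. Analysing cross-ins as randomized is correct for mITT, and the sample size and significance level are unaffected. Severity is low.

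**What to change.** In SAP 6.1.2:

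1. **Appointment window.** Count attended PT visits after Day 1 through the Day 60 assessment, in the same way in both arms. Section 3 of the protocol lists visit totals and episode dates but no date for each visit. If dated visits cannot be extracted, use total visits attended minus visits 1 and 2. That fallback cannot enforce the Day 60 end, but the episode end date can flag counts that may run past it.
2. **PT-only condition.** Require no reported TENS use before the Day 60 assessment, based on the planned completion question and clinic CPT codes. Under that wording a participant with no answer is retained; say so and report how many there are.
3. **Reporting.** Give the PP result with and without the PT-only condition, beside mITT, and label it a non-randomized sensitivity comparison. Selection of adherers in the TENS arm remains in either version.

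The cost is mainly SAP wording. The condition relies on late self-report that may be missing for some, and the control set becomes slightly smaller. Rewording the completion question to cover the period before Day 60 would need cIRB approval and would miss participants who have already finished. Dated visits may need an addition to the EHR extraction.

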### **1.3 Interventions and Duration**

For the TENS+PT group, participants will be given TENS devices and electrodes following enrollment (signed consent) during their second PT visit. TENS will be applied to the upper and lower back with butterfly electrodes using the following parameters: mixed frequency (2-125Hz), strong but comfortable intensity, variable pulse duration from 100-250 microseconds. TENS will be applied for 2 hours per day at home when the patient is active and doing exercises and should be brought back to PT visits and used during PT treatment.

For the PT only group, participants will be given TENS units after the primary endpoint is collected at 60 days. The same parameters and instructions will be given to the participants as were given to the participants in the TENS+PT group. However, TENS instructions will be done virtually with a study team member rather than in person by their physical therapist.

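### In the TENS arm, per-protocol membership can turn on TENS use after the primary rating when that rating is made on days 55 to 59

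*SAP*

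**What the plan says.** SAP 6.1.2 sets two usage conditions for the TENS arm. The first is "Used TENS on at least 8 days within the first 30 days following day 1 homework assignment", with at least 900 minutes in that period. The second is "Used TENS on at least 8 days during the subsequent 30 days (days 31–60", again with 900 minutes, worded as "have accumulated a minimum of 15 hours of TENS use during days 31 to 60". The SAP says that the conditions "assure continuous adherence of TENS use over the 60-day period". The PT-only arm has no usage condition. TENS participants who fail the rule go into a dose-response analysis, in groups defined by the same two periods.

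The primary rating has its own window. SAP Table 5.1 lists "V02 (Day 60 -5/+10) Primary Endpoint", and Protocol 6.1 and 6.2.5 give the same limits. TENS-arm participants go on using the device to day 180 (Protocol 5.1). Neither document ends the usage count at the rating or limits the per-protocol set to ratings made on or after day 60.

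The visit clock is worded in two ways. SAP 1.1 describes "data collection from home at 1, 30, 60, 90, and 180 days following enrollment", and SAP 1.3 has devices handed out "following enrollment (signed consent) during their second PT visit". Protocol 6.1 instead makes Day 1 the day of the home baseline and adds: "Baseline data collection should be completed within 10 days of the second PT visit".

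**The concern.** The per-protocol set is used to repeat the key effectiveness analyses among participants who adhered. If someone is rated on day 55, use on days 56 to 60 cannot have influenced that rating but still counts towards membership. Later use may itself respond to the pain just recorded, and staff contact participants whose use is low (Protocol 6.2.15). Two participants with the same use and the same rating on day 55 can therefore be classified differently because of what they did afterwards. As only the TENS arm is filtered on use, any such selection acts on one side of the comparison. The dose-response groups inherit it.

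**Working it through.** **Inputs**
- Second usage window: days 31 to 60 after the Day 1 homework, with at least 8 days and 900 minutes of use (SAP 6.1.2).
- Rating window: 60 − 5 = day 55 to 60 + 10 = day 70 (SAP Table 5.1; Protocol 6.1, 6.2.5).
- Planned daily use: 2 hours = 120 minutes (SAP 1.3), taken here as the ceiling per day.

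**The plan's own figure.** 0.5 h × 30 = 15 h = 900 minutes. It reproduces exactly.

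**Overlap, with visits counted from Day 1.** For a rating on day r, counted days after the rating = max(0, 60 − r). The most minutes they can supply = 120 × (60 − r). The rating day itself is treated as before the outcome.

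| Rating day | Counted days after rating | Maximum minutes after rating | Share of 900 minutes | Share of 8 days |
|---|---|---|---|---|
| 55 | 5 | 600 | 67% | 63% |
| 57 | 3 | 360 | 40% | 38% |
| 59 | 1 | 120 | 13% | 13% |
| 60 to 70 | 0 | 0 | 0% | 0% |

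At the earliest permitted rating, 5/30 = 17% of the window falls after the outcome.

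**Can it change membership?** Yes, in both directions. Take a rating on day 55, 25 days into the window.
- Someone using exactly 30 minutes a day has 25 × 30 = 750 minutes at the rating. The remaining 900 − 750 = 150 minutes, all after the outcome, decide inclusion. If use stops after the rating, the person is excluded.
- Someone with only 900 − 600 = 300 minutes at the rating, on 3 days (an average of 300/25 = 12 minutes a day over the 25 days), can still reach 900 minutes and 8 days by using TENS for 2 hours on each of days 56 to 60.

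**Late ratings.** For ratings on days 61 to 70 no later use is counted. Up to 10 days of use before the rating are ignored, but that is not selection on post-outcome behaviour.

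**Separate assumption: visits scheduled from enrollment.** Suppose consent is at Visit 2 and Day 1 falls L days later, with L from 0 to 10. A rating on day 55 of that clock is day 55 − L after Day 1, so the overlap is 60 − (55 − L) = 5 + L days, or 5 to 15. With L of 5 or more, 10 or more counted days follow the earliest permitted rating. They can supply 10 × 120 = 1,200 minutes or more, so the whole second-period requirement could be met after the outcome.

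Whether the first period is read as days 1 to 30 or days 2 to 31 moves these counts by at most one day.

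**The case against.** The strongest reply is that a single fixed 60-day definition is a deliberate and defensible choice. The SAP's stated aim is adherence over 60 days, not adherence up to the rating, and one set serves several outcomes. Any usage-based set also selects on behaviour after randomisation in one arm. Use on days 31 to 54 may respond to symptoms too, so trimming five days at most leaves most of that selection in place. All of this stands, and it limits the weight of the point. It does not explain why use that came after the outcome should count.

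A reader might infer that half the second window (15 of 30 days) follows the outcome and that the baseline-to-endpoint interval runs from 45 to 70 days. The documents do not support this as the main reading. Protocol 6.1 defines Day 1 as the home baseline and sets the later visits out in the same schedule, and SAP Table 5.1 puts baseline (Day 1) and Day 60 on one scale. The SAP 1.1 sentence itself lists day 1 among the days after enrollment. Taken literally from consent, a baseline ten days later could not be day 1, so enrollment looks loosely used. Even on the enrollment clock, 15 days is not a strict bound, because consent is planned before Visit 2 (Protocol 4.3, 6.2.1). The 45-to-70 interval also needs the full range of lags: a fixed 10-day lag gives 45 to 60.

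A reader might also infer that the trial's main result is at risk. It is not, because the primary analysis uses the modified intention-to-treat population regardless of device use (SAP 1.1, 6.1.1).

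**Conclusion.** The point holds as a minor improvement to a sensitivity population. With visits counted from Day 1, 1 to 5 of the 30 days in the second window fall after the primary rating for participants rated on days 55 to 59. At 2 hours a day those days could supply up to 600 of 900 minutes and 5 of 8 days, which is enough to decide membership. Only the TENS arm of the per-protocol analysis and the dose-response groups are touched. The documents give no distribution of rating dates or usage, so the number of participants affected, which could be zero, and the direction of any bias cannot be computed. The 5-to-15-day overlap rests on the added assumption of an enrollment clock and should be read only as a reason to state the clock.

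**What to change.** 1. **SAP 6.1.2, second window.** End it at the earlier of day 60 and the participant's primary Day 60 rating. Where this shortens the window, prorate the thresholds: 30 minutes × days in the window, and 8/30 of the days. A rating on day 55 gives 30 × 25 = 750 minutes and 25 × 8/30 = 6.7 days, so the rounding rule should be stated.
2. **Everyone else.** Keep days 31 to 60 and the present thresholds for participants rated on or after day 60. Extending the window to a rating on day 70 would raise the requirement to 30 × 40 = 1,200 minutes with no post-outcome use to remove. Keep them also for participants with no Day 60 rating, who remain in the modified intention-to-treat population through imputation (SAP 7.3) and have no rating date at which to cut.
3. **Dose-response groups.** Apply the same cut-off.
4. **Both documents.** State that visit windows count from Day 1. Because the cut-off in item 1 follows the actual rating date, it removes the overlap on either clock.

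The cost is SAP wording and a small programming change, ideally made before the per-protocol set is derived. Early raters are judged on a slightly shorter adherence window. Device data must be available by day: Protocol 10.2.1 describes stored minutes per week, which needs checking, although the existing 8-day rule already requires daily records.
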